The attributes of the main estimand (target of estimation), used for the primary analysis of the highest ranked efficacy endpoint (modified Rankin Scale (mRS) score) are defined below. Although the primary objective of this study is related to safety, analysis of the efficacy endpoints (secondary objectives of the study) will be based on a pre-defined hierarchy and therefore, an estimand is defined.

- The **population** is defined as the intent-to-treat study population (see Section 3.2.3).
- The corresponding **variable** to be obtained for each subject required to address the scientific question is disability based on the mRS score at Day 90. The mRS will be evaluated as a binary outcome (0-2, 3-6).
- The **population level summary** considered in this study is the odds ratio between RNS60 1.0 mL/kg/h and placebo 1.0 mL/kg/h.
- The **treatments** to be compared are RNS60 1.0 mL/kg/h and placebo 1.0 mL/kg/h. The treatments will be compared according to the randomized groups, regardless of the treatment that was actually received. In accordance with the treatment policy principle, all available data will be used in the analysis, regardless of e.g., premature discontinuation of study medication or administration of any concomitant treatment.
- The **intercurrent events** (ICEs) considered as potentially impacting results and/or interpretation are:
 - Premature discontinuation of study treatment
 - Death
 - Coronavirus Disease 2019 (COVID-19) pandemic related events (assessments that were missed due to COVID-19).

For the data that are missing due to premature discontinuation of study treatment, an assumption of Missing At Random (MAR) will be made. Sensitivity analyses will be conducted using an assumption of Missing Not At Random (MNAR). No specific imputation will be done for these missing data, because the likelihood-based analysis approach can manage subjects with incomplete data under the assumption of MAR.

For the data that are missing due to COVID-19, an assumption of MAR will be made for all analyses, both primary and sensitivity analyses.

For the mRS, NIHSS and BI endpoints death is included as part of the scoring, so no imputation of these endpoints is required for subjects who die. Similarly, for the worsening of stroke endpoint, death represents a worsening. For the infarct progression end point, death will be represented by a missing value.

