In addition to the primary time point of each endpoint (as defined below), all other applicable time points will be compared as well and interpreted in an exploratory manner.

In these analyses, testing the combined-dose versus placebo will be done within the statistical models by averaging the results in the two active doses and comparing to placebo. (This is in contrast to performing a separate analysis in which subjects on active dose are treated as a single treatment arm.)

Generalized linear mixed models will be implemented for the analyses of disability based on mRS, infarct volume, NIHSS at 24 hours, worsening of stroke, and Barthel Index. NIHSS will be analyzed on the recorded scale of measurements and the treatment groups' Least Squares (LS) means, corresponding 95% confidence intervals (CIs), and LS mean differences will be reported. Disability based on mRS, worsening of stroke, and Barthel Index are dichotomized endpoints that will be analyzed on the logit scale of measurement. The resulting LS means and confidence intervals will be back-transformed to probabilities, and differences in least squares means will be reported as odds ratios. Infarct volume will be analyzed as log-normally distributed, and descriptive statistics will be geometric means where between-group comparisons will be reported as ratios of geometric means. Covariates baseline NIHSS and ASPECTS binary factors for efficacy analysis will use baseline values from the Electronic Data Caputre.

1. Modified Rankin Scale (mRS) score:

The effect of treatment on global disability at Day 90 will be examined by comparing the proportion of subjects who had disability (Yes or No) between the three treatments (RNS60 1.0 mL/kg/h, RNS60 0.5 mL/kg/h, and placebo 1.0 mL/kg/h) using generalized linear mixed modeling (GLM) using residual pseudo-likelihood with a subject-specific expansion(RSPL) assuming a binary outcome (0-2=0, 3-6=1). Covariates include the Age, baseline NIHSS, and ASPECTS binary factors used for block urn randomization and baseline (pre-morbid) mRS, baseline occlusion location, study site, baseline perfusion status, and log of baseline infarct volume. Treatment, visit day, and interaction of treatment and visit day are included as categorical fixed effects.

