An unstructured covariance structure will be applied for GLM. In case the model will not converge with the unstructured covariance structure, Heterogeneous Autoregressive (1) (ARH(1)), Heterogeneous Compound Symmetry (CSH), Autoregressive(1) (AR(1)) or Compound Symmetry (CS) covariance structure will be used instead in this order until convergence is achieved.

The predicted probability for each treatment group and least squares (LS) mean difference between high-dose and placebo and low-dose and placebo groups along with the 95% confidence intervals (CIs) for Day 90 will be provided using the LSMEANS/DIFF statement with the ILINK option. The comparison of the two combined active arms versus placebo will be performed using the LSMESTIMATE statement. The odds ratio will also be calculated. The P-value for the hypothesis testing will also be provided. Treatment difference will be assessed with a 2-sided alpha level of 0.05, verifying, however that any statistically significant finding is consistent with the alternative hypothesis of efficacy versus placebo.

The sample SAS code planned for the analysis is outlined below.

Summary of dichotomized mRS endpoint (0-2 indicating a value of 0 and 3-6 indicating a value of 1) with counts and percentages of subjects will be generated to compare baseline mRS with Day 90 for each treatment arm and for the two active arms combined.

Horizontal bar graphs will be generated to visualize mRS distribution at Day 90 across all treatment groups. mRS score at Day 90 will be displayed where bars will be labelled with subject counts and proportions.

KEY SENSITIVITY ANALYSIS (analysis assuming Missing Not At Random (MNAR))

The analysis consists of the following steps:

1. Imputation of all intermittent missing data with multiple imputation (MI) assuming MAR, in order to generate a dataset with monotone missing data structure. The endpoint being modeled will be the mRS on the original 0-6 scale, rather than the derived binary endpoint.
2. Based on dataset generated in Step 1: imputation of all monotone missing data with MI assuming MAR, in order to generate dataset with no missing data
3. Based on dataset generated in Step 2 (with no missing data): all visits that have monotone missing data that are not due to COVID-19 will be set back as missing for subjects in the active arm.

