The dataset generated in Step 3 (which contains monotone missing data) will be imputed based on the assumption of MNAR, using Copy-Reference imputation. The MNAR imputation will be based on trajectories in the placebo group, i.e., data from the placebo group only will be used to generate the imputations. This step will include data for active subjects identified in step 3 along with all placebo subjects. For this, the MNAR statement will be used as described below.

Step 5: Analysis of imputed data with GLM

The imputed datasets generated in Step 4 do contain only non-missing values and are used as input in the statistical model. The final step before statistical inference is to convert the imputed mRS data (on the 0-6) scale to the binary endpoint (0-2, 3-6). Residual pseudo-likelihood with a subject-specific expansion (RSPL) based GLMs will be run on each of the 500 generated imputed datasets. For additional details on how to specify the GLM, see the analysis section corresponding with this sensitivity analysis.

Step 6: Combination of results from the GLMs

Finally, the MIANALYZE procedure in SAS will be applied to combine the 500 results from the analyses generated in Step 4, to derive an estimate of the treatment difference at day 90. In addition to the estimate, corresponding two-sided 95% CIs and p-values will be generated with the MIANALYZE procedure.

2. Volume of stroke or Infarct volume (Diffusion-weighted imaging, DWI):

Infarct progression/regression will be analyzed as measured by MRI brain imaging. Where MRI was not available, infarct volumes will be obtained from a 48-hour CT imaging. Infarct volume will

be summarized with descriptive statistics at Baseline, 24 hour, 48 hour, and Day 90 timepoints. The volume difference between 48 hour and 24 hour and between Day 90 and 24 hour timepoint will also be summarized.

The simple effect of treatment on Infarct progression/regression will be examined by 48-hour infarct volume on a log scale between the three treatments (RNS60 1.0 mL/kg/h, RNS60 0.5 mL/kg/h, and placebo 1.0 mL/kg/h) using GLM using maximum likelihood assuming a Gaussian distribution. Covariates include the log of baseline infarct volume along with Age, baseline NIHSS, ASPECTS binary factors used for block urn randomization, baseline perfusion status, baseline occlusion location, and study site.

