Additionally, neurological functioning at Day 90 will be examined by NIHSS scores at Day 90 between the three treatments (RNS60 1.0 mL/kg/h, RNS60 0.5 mL/kg/h, and placebo 1.0 mL/kg/h). GLM analysis and missing data imputation analysis at Day 90 will be performed using the same approach described above for neurological functioning using 24-hour NIHSS scores.

4. The proportion of subjects with worsening of stroke over the 48-hours/duration of admission:

Worsening of stroke is defined (i.e., Yes or No) as: progression, or hemorrhagic transformation, of the index stroke as documented by medical imaging and that is (a) life-threatening requiring intervention and/or (b) results in increased disability as gauged by a \geq 4-point increase from lowest NIHSS pre decline and/or (c) results in death. Subjects with worsening of stroke will be identified based on a \geq 4-point increase in their worst minus best NIHSS score and adverse events status (life threatening requiring intervention or death) as collected in the CRFs.

The simple effect of treatment on worsening stroke at 48 hours/admission duration will be examined by comparing the proportion of subjects who had worsening stroke (Yes or No) between the three treatments (RNS60 1.0 mL/kg/h, RNS60 0.5 mL/kg/h, and placebo 1.0 mL/kg/h) using GLM using residual pseudo-likelihood with a subject-specific expansion (RSPL) assuming a binary distribution. Covariates include the Age, baseline NIHSS, and baseline ASPECTS as binary factors used for block urn randomization, log of baseline infarct volume, baseline perfusion status, baseline occlusion location, and study site.

The predicted probability for each treatment group and LS mean difference between high-dose and placebo and low-dose and placebo groups along with the 95% CIs will be provided using the LSMEANS/DIFF statement. The comparison of the two combined active arms versus placebo will be performed using the LSMESTIMATE statement with the ILINK option. The odds ratio will also be calculated. The P-value for the hypothesis testing will also be provided. Treatment difference will be assessed with a 2-sided alpha level of 0.05.

The sample SAS code planned for the analysis is outlined below.

5. Barthel Index.

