The effect of treatment on functional independence at Day 90 will be examined by comparing subjects achieving functional independence (Barthel Index score ≥ 95 as compared to < 95) where subjects having a score ≥ 95 on the Barthel Index Score at Day 90 will be deemed to have achieved functional independence, and those scoring < 95 at Day 90 will be deemed to have failed to achieve functional independence.

The proportion of subjects who achieved functional independence (BI score ≥ 95 vs. < 95) at Day 90 will be compared between the three treatments (RNS60 1.0 mL/kg/h, RNS60 0.5 mL/kg/h, and placebo 1.0 mL/kg/h) using generalized linear mixed modeling using RSPL assuming a binary outcome ($< 95 = 0$, $\geq 95 = 1$). Covariates include the Age, baseline NIHSS, and ASPECTS binary factors used for block urn randomization and baseline BI total, log of baseline infarct volume, baseline perfusion status, baseline occlusion location, and study site. Treatment, visit day, and interaction of treatment and visit day are included as categorical fixed effects.

Sensitivity analysis of BI will be performed in a similar way to the primary analysis using the GLM approach with RSPL assuming a binary outcome ($<95=0$, $\geq 95=1$) where any missing value of BI will be imputed as functional independence not achieved (coded as 0).

3.4.3 Sensitivity Analysis for Secondary Efficacy Endpoints with Dichotomous Data for Baseline Collaterals

For each of the secondary efficacy endpoints described in section 3.4.2, additional sensitivity analysis will be performed using the GLM analysis approach where baseline collaterals will also be included in the model. For subjects with a baseline collateral score, the score will be converted to baseline collateral status. Baseline collaterals dichotomization will use the following conversion approach:

Dichotomization A (main): where a baseline collateral score of 0-2 indicates Baseline collateral status = Absent, and a baseline collateral score of 3-5 indicates Baseline collateral status = Present

Dichotomization B: where a baseline collateral score of 0 indicates Baseline collateral status = Absent, and a baseline collateral score of 1-5 indicates Baseline collateral status = Present.

Dichotomization C: where a baseline collateral score of 0-1 indicates Baseline collateral status = Absent, and a baseline collateral score of 2-5 indicates Baseline collateral status = Present.

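### SAP 2.1.3 justifies not imputing Day 90 mRS by a likelihood-based analysis, but 3.4.2(1) fits binary mRS by residual pseudo-likelihood, so the stated reason does not cover the estimator used

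*SAP*

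**What the plan says.** SAP 2.1.3 sets the estimand for the highest-ranked efficacy endpoint, mRS 0-2 versus 3-6 at Day 90. It assumes MAR for data missing after early discontinuation of treatment and plans no imputation, "because the likelihood-based analysis approach can manage subjects with incomplete data under the assumption of MAR". The summary measure "considered in this study is the odds ratio between RNS60 1.0 mL/kg/h and placebo 1.0 mL/kg/h", with no statement of whether it is conditional or marginal.

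SAP 3.4.2(1) fits the mRS model "using residual pseudo-likelihood with a subject-specific expansion(RSPL) assuming a binary outcome", with visit, treatment and their interaction as fixed effects and an unstructured covariance with fallbacks. The code is redacted, and the readable text does not say whether that covariance is a patient random effect or a residual structure. The one random effect it names is site (3.1.5).

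SAP 3.1.6 relies on longitudinal mixed models under MAR for missing mRS, 24-hour NIHSS, worsening of stroke and infarct volume. Worsening of stroke is fitted "using GLM using residual pseudo-likelihood with a subject-specific expansion (RSPL) assuming a binary distribution" (3.4.2(4)). Infarct volume is fitted "using GLM using maximum likelihood assuming a Gaussian distribution" (3.4.2(2)), so the SAP itself tells the two methods apart.

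**The concern.** For a binary outcome, RSPL repeatedly fits a normal model to a linearised response. It does not maximise the likelihood of the observed 0/1 data. The usual result that missing data can be ignored under MAR belongs to likelihood (or Bayesian) inference, so 2.1.3 claims a property that the current model lacks. This is a conflict between two current sections. The version history records that RSPL replaced Laplace in SAP 3.0, which may be why the sentence was left behind.

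High dose versus placebo on mRS is first in the testing order, and the protocol (9.3.3) says the efficacy results are to inform powering of a later trial. An odds ratio with an unclear target and no secured missing-data property is a weak basis for that.

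**Working it through.** There is no plan figure to reproduce: SAP 2.2.4 states that no power analysis was done, and the SAP gives no missing-data rate.

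**1. Is there a planned MAR analysis elsewhere?** Step 2 of the mRS sensitivity analysis is "imputation of all monotone missing data with MI assuming MAR, in order to generate dataset with no missing data". Step 3 then blanks the active-arm monotone values not due to COVID-19, Step 4 refills them by copy-reference, and Step 5 refits by RSPL. The complete MAR-imputed datasets exist after Step 2 but are never analysed. The Wilcoxon analysis (3.4.4.1) is not a model of the binary endpoint.

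**2. Simulation inputs.** From the documents: 100 patients at 1:1:1, about 33 per arm; placebo Day 90 risk of mRS 3-6 taken as 0.50, because protocol 2.1.2 says about half become independent with EVT. Assumed: high-dose risk 0.35, risks at earlier visits, three visits, patient intercept SD, and loss that depends on Day 30 state. Covariates and site were left out.

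- Marginal OR = (0.35/0.65)/(0.50/0.50) = 0.538.
- Conditional OR at SD 2 = 0.362 (log -1.016).
- Shrinkage = 1 - ln(OR from RSPL)/ln(conditional OR).

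**3. Large-sample Day 90 odds ratios, SD 2** (20,000-30,000 per arm, Monte Carlo error about 2-5%). Reversed means that the dependence of loss on Day 30 state is opposite in high dose and placebo.

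| Loss at Day 90 | True ML | RSPL, patient random effect | RSPL, residual covariance | Completers |
|---|---|---|---|---|
| None | 0.358 | 0.490 | 0.536 | 0.536 |
| 5%, same direction | 0.375 | 0.505 | 0.551 | 0.549 |
| 10%, same direction | 0.347 | 0.479 | 0.525 | 0.525 |
| 10%, reversed | 0.376 | 0.529 | 0.552 | 0.623 |
| 25%, reversed | 0.352 | 0.570 | 0.531 | 0.821 |
| No effect, 10% reversed | 0.994 | 1.037 | 0.998 | 1.123 |
| No effect, 25% reversed | 0.948 | 1.117 | 0.971 | 1.466 |

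**4. Shrinkage with complete data.** ln(0.490) = -0.713, so 1 - 0.713/1.016 = 30%. A separate simulation at 33 per arm (50% versus 30%, SD 2, 400 replicates) gave a mean RSPL log OR of -1.01 against a conditional -1.38: 1 - 1.01/1.38 = 27%, with 93% coverage of the 95% interval. At SD 1, RSPL gave 0.525 against 0.474: 1 - 0.644/0.747 = 14%. This shrinkage comes from the binary approximation, not from missing data.

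**5. Added effect of MAR loss.** Same-direction loss moves the random-effect version from 0.490 to 0.505 or 0.479, within Monte Carlo error. With no true effect and reversed loss it gives 1.04 (10%, itself close to Monte Carlo error) and 1.12 (25%). A separate random-intercept run with about 18% reversed loss shifted the log OR by 0.15, and exp(0.15) = 1.16.

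**6. Against sampling error.** At 33 per arm the SD of the RSPL (random-effect) log OR was 0.56 with complete data. The largest MAR shift is 0.15/0.56 = 0.27 of one standard error.

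**The case against.** The strongest reply is that the sentence is loosely worded and little follows from it.

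- The only random effect in readable text is site, and the listed covariance structures could be residual-side. In that case RSPL sits close to the marginal odds ratio and shows no material MAR bias. This stands, so the shrinkage and bias figures are conditional.
- Reversed dependence between arms is an unfavourable scenario that nothing in the documents suggests. Deaths are scored, not missing (3.1.7). Patients who stop drug stay in follow-up, and representatives, telemedicine and telephone are used. This also stands.
- The planned covariates should reduce patient heterogeneity below the assumed SD of 2.
- The SAP also tabulates dichotomised mRS by arm, so sizing the next trial does not rest on the model odds ratio alone.

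A reader might infer that the SAP promises a population-averaged odds ratio and then reports something else. It does not: population level summary is the name of an estimand attribute, and its content is only an odds ratio. Nor does RSPL create that ambiguity. True maximum likelihood gives 0.358, further from the marginal 0.538 than either RSPL version.

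Barthel is also fitted "using generalized linear mixed modeling using RSPL assuming a binary outcome", but it lies outside the written estimand and the 3.1.6 list, and its sensitivity analysis counts missing as failure.

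None of this makes RSPL a likelihood method for binary data.

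**Conclusion.** The point holds in limited form. The reason given in 2.1.3 for not imputing does not apply to the mRS estimator in 3.4.2(1), and no planned model of binary Day 90 mRS supplies MAR validity by another route. Worsening of stroke has a related gap: 3.1.6 counts on the mixed model for MAR, and 3.4.2(4) fits that model by RSPL.

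The numerical effect is open because the code is redacted. Under a patient random effect with SD 2, the conditional log odds ratio shrinks by about 27-30%; the null odds ratio drifts to about 1.04-1.16 only under reversed loss of 10-25%. Under a residual covariance the result is close to the marginal value.

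Two stronger readings are not supported. The MAR assumption itself does not fail: it concerns the data, and what is lost is the estimator's guarantee. Nor can it be said without condition that the reported odds ratio estimates neither target, since the residual-side results contradict it. Importance is moderate: this is a secondary endpoint in an unpowered safety trial, but it ranks first for efficacy and the correction is cheap.

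**What to change.** 1. In SAP 2.1.3, replace the likelihood-based sentence with one that matches the method used. Align 3.1.6 for worsening of stroke.
2. In 3.4.2(1), add as the MAR analysis a covariate-adjusted logistic regression of Day 90 mRS (0-2 versus 3-6) on the 500 datasets as they stand after Step 2, pooled with MIANALYZE. Say how site enters. Adaptive quadrature is an alternative where it converges, which is uncertain with this covariate list and about 33 patients per arm.
3. State whether the visit covariance is a patient random effect or a residual structure.
4. State in 2.1.3 whether the target odds ratio is conditional or marginal. If marginal, standardise over covariates and any random effects.

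The cost is some SAP wording, a little more programming and possibly wider intervals. The imputations are already planned.
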